Assess other possible confounders (not included in main analyses due to power limitations):

We will perform a sensitivity analysis for the main analysis (1, 2A and 2B), with the same statistical model but only including covariates with statistically significant beta coefficient in the corresponding main analysis, and depending on available number of further covariates (given maximum eight), the

Statistical Analysis Plan for analysis of cytokines as prognostic factors and predictors of antibiotic treatment effect in patients with chronic low back pain and Modic changes (the AIM trial) - - version 1.0

following covariates will be considered: treatment group (amoxicillin/placebo), comorbidity, NSAIDs use (at baseline and one-year follow-up), physical workload, sleep disturbance(64), BMI, smoking, LBP intensity at baseline (0-10 NRS), and prior surgery for disc herniation. Each sensitivity analysis will be compared to their respective main analysis by assessing R^2 .

The following sensitivity analyses will be considered performed:

Assess the possibility of non-linear effects of the cytokine

For each main analyses 5 (A-E), we will consider using a correspondent multivariable fractional polynomial (MFP) model or other polynomial regression model (73). All covariates of the original regression analyses will be forced included (by setting nominal p-values for variable selection to one in MFP model), only the independent variable of interest will be tested for a non-linear relationship (degrees of freedom for other continuous variables will be set to one) with (for MFP) standard powers (-2, -1, -0.5, 0, 0.5, 1, 2, and 3) and a fractional polynomial election significance level of 5% (using the mfp command in Stata). Each MFP model will be compared to its respective main analysis by assessing R^2 .

Independence of effect:

In the case of statistically significant association between the relative change in RMDQ from baseline to one-year follow-up and the independent variables in analyses 1 to 5, we will assess the independence of any effect by including all variables significantly associated with outcome into the same model. We will add the following as covariates into the model due to possible confounding (same as above) but will consider leaving out some covariates if many cytokines are included: age, leg pain (0-10 NRS), fear avoidance, emotional distress, comorbidity, physical workload, and sick leave. We will also consider selecting out any cytokines in the model that are highly correlated.

Further tables and figures

Table 4 - Criteria for evaluating the results of the present analyses of potential predictors of treatment effect

When interpreting the plausibility of any potential predictors of treatment effect, we will use the following criteria for evaluating subgroup analyses (59) (currently known answers for present analysis in parentheses):

Design

Is the subgroup variable a characteristic measured at baseline or after randomisation?* (At baseline)

Is the effect suggested by comparisons within rather than between studies?

Statistical Analysis Plan for analysis of cytokines as prognostic factors and predictors of antibiotic treatment effect in patients with chronic low back pain and Modic changes (the AIM trial) - - version 1.0

Was the hypothesis specified a priori? (Partly. The hypotheses were specified before any analyses described in the current SAP were performed, but after results for treatment efficacy in the main trial (5) and in clinical and radiological subgroups (6, 7) were available)

Was the direction of the subgroup effect specified a priori?* (Yes)

Was the subgroup effect one of a small number of hypothesised effects tested?

Analysis

Does the interaction test suggest a low likelihood that chance explains the apparent subgroup effect?

Is the significant subgroup effect independent?*

Context

Is the size of the subgroup effect large?

Is the interaction consistent across studies?

Is the interaction consistent across closely related outcomes within the study?*

Is there indirect evidence that supports the hypothesised interaction (biological rationale)?

*New criteria.

Table 5A – Distribution of baseline cytokine categories by treatment group

| Variable | Amoxicillin group (N = 46) | | Placebo group (N = 32) | |
|--|-------------------------------|-----|---------------------------|-----|
| | n | % | n | % |
| Cytokine category, used for analyses 2 (A and B) | | | | |
| category 1 | 5 | 11 | 3 | 9 |
| category 2 | 19 | 41 | 10 | 31 |
| category 3 | 13 | 28 | 7 | 22 |
| category 4 | 9 | 20 | 12 | 38 |
| Sum | 46 | 100 | 32 | 100 |

[figure not shown]
Table 5B – Distribution of baseline cytokine categories by treatment group in those with nonmissing values for RMDQ at baseline and 1 year follow-up

| Variable | Amoxicillin group (N = 45) | | Placebo group (N = 27) | |
|--|-------------------------------|-----|---------------------------|-----|
| | n | % | n | % |
| Cytokine category, used for analyses 2 (A and B) | | | | |
| category 1 | 5 | 11 | 3 | 11 |
| category 2 | 19 | 42 | 9 | 33 |
| category 3 | 13 | 29 | 6 | 22 |
| category 4 | 8 | 18 | 9 | 33 |
| Sum | 45 | 100 | 27 | 100 |

Table 5C – Distribution of baseline cytokine categories by treatment group in compliers

| Variable | Amoxicillin group (N = 41) | | Placebo group (N = 24) | |
|--|-------------------------------|-----|---------------------------|-----|
| | n | % | n | % |
| Cytokine category, used for analyses 2 (A and B) | | | | |
| category 1 | 5 | 12 | 3 | 13 |
| category 2 | 18 | 44 | 8 | 33 |
| category 3 | 12 | 29 | 5 | 21 |
| category 4 | 6 | 15 | 8 | 33 |
| Sum | 41 | 100 | 24 | 100 |

Figure 3 - PCA biplot of serum cytokine levels in healthy controls and patients with MCs

References

3. Riley R. PROGRESS (PROGnosis RESearch Strategy) 2020 [Available from: <https://www.prognosisresearch.com/>].

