Analyses of predictors of treatment effect (hypothesis 1) and of prognostic factors (hypothesis 2) will be based on imputed values unless stated otherwise. Missing RMDQ, ODI, LBP intensity and fear avoidance values will be imputed. For RMDQ we will first perform a mean imputation at any timepoint in those cases where less than 30% of the questions are missing and secondly a multiple imputation in those cases where more than 30% of the questions are missing at any timepoint. The multiple imputation model will use predictive mean matching. We will impute both RMDQ and LBP intensity at baseline, 3 months, 6 months, 9 months and 12 months, ODI score at baseline, 3 months

and 12 months, and fear avoidance at baseline, using index EQ5D-5L score (at baseline, 3 and 12 months), and the following baseline variables: age, leg pain (NRS 0-10), comorbidity (Functional Comorbidity Index), emotional distress, physical work load, psychiatric comorbidity (yes/no), other specific comorbidity (numerical, one point for each of rheumatoid arthritis, osteoarthritis, Diabetic, Cardiac/pulmonary), sick leave, NSAIDs use (at baseline and one-year follow-up), sleep disturbance, BMI, smoking, former surgery for disc herniation, study center, Modic type group, STIR composite group, cytokine classification group, principal component 1 (from analyses 3 A and B under analyses of hypothesis 1), treatment group, and the interaction terms cytokine classification group x treatment, principal component 1 (for 3A) x treatment and principal component 1 (for 3B) x treatment as predictors in the imputation model. The imputation model can be reduced if the imputation does not converge. Fifty imputations will be performed(55) and the imputation model will include the same patients who are included in the analysis (n=78).

Analyses of cytokines as predictors of antibiotic treatment effect (hypothesis 1)

Descriptive statistics

We will present the heatmap and dendrogram in figure 2, with the same order of patients and cytokines (based on analysis performed for figure 2), but with an additional color-coded marker row for treatment group, including a color-coded bar classifying patients into 1 ($\leq 30\%$ improvement of RMDQ from baseline to 1 year), 2 ($>30\%$ and $\leq 50\%$ improvement of RMDQ from baseline to 1 year), 3 ($>50\%$ and $\leq 75\%$ improvement of RMDQ from baseline to 1 year), 4 ($>75\%$ improvement of RMDQ from baseline to 1 year).

Inferential statistics

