To explore potential predictors of treatment effect we will perform six main analyses (1A, 1B, 1C, 2A, 3A, 3B) of predictors of antibiotic treatment effect (Table 2). All six analyses will be performed using multiple regression with RMDQ score at one year as dependent variable and the interaction term (predictor*treatment group) as independent variable adjusted for baseline RMDQ score, the potential predictor, the treatment group, the randomization stratification variables (MC type (1/2) and for former disc herniation surgery (yes/no)).

We will only use the baseline value for any potential predictor of treatment effect and for any covariate. Within each category (subgroup) of categorical variables, we will report the treatment effect predicted in the interaction term analysis by marginalizing (using the margins command in Stata) over the other covariates (and not perform a separate stratified analysis).

We will present results of analyses 1A, 1B, 1C, 2A, 3A and 3B in a forest plot of effect estimates for each potential predictor of treatment effect with 95 % CIs and the p value for the interaction (predictor *treatment group). The overall treatment effect will be marked on the plot (56). The plot will also show the treatment effect within subgroups.

Table 2 –Main analyses of cytokine-defined predictors of treatment effect

| Hypothesis and rationale | Variables and subgroups | Analysis |
|--|---|---|

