- A. Variables will include cytokines with levels that were significantly different from the healthy controls (CCL11, CCL22, CCL21, IL4, CCL26, IL6, CXCL13, CX3CL1, CCL27, CXCL6, CCL20, IFN γ , CCL19, IL2, CCL17, IL16, CCL25, CCL7, CCL13, MIF, CCL3, CCL15, CCL23, CXCL16).
- B. All 39 cytokines are included as variables.

These stage 1 analyses are already performed prior to publication of this SAP, giving a proportion of variance explained by principal component 1 of 34.9% in analysis A and 31.4% in analysis B.

In stage 2, a regression analysis (as described above) will be performed, where the potential predictor of treatment effect of interest will be defined as the principal component 1 from the stage 1 analyses A and B. Both stage 1 analyses (A and B) will result in one regression analysis that we will perform in prioritized order (3A and 3B, respectively).

Supportive and sensitivity analyses

As supportive analyses for 1 (A, B and C), we will perform:

- I. Analyses with LBP intensity and ODI score at one year as dependent variables to assess if any subgroup effect is consistent across related outcomes, as recommended (59).

If clinically important differences between the treatment groups in analysis 1 (A, B and C), we will also perform the following supportive analyses:

- II. Analyses with RMDQ score at 3 months follow-up as dependent variable, otherwise similar as above.
- III. Responder analyses with responders defined as >30%, >50% and >75% improvement in RMDQ from baseline to one year, including calculation of numbers needed to treat. For these analyses we will consider >50% and >75% improvements as more likely in any underlying infection (discitis).
- IV. Linear mixed effects (LME) models with RMDQ as dependent variable, and 3-part interaction term time x treatment group x cytokine classification group (treating time as a categorical variable), adjusted for MC type (1/2) and for former disc herniation surgery (yes/no). All LME model specifications will be selected based on Akaike's Information Criterion. Based on the selected model, we will do a pairwise comparison of marginals to estimate the treatment effect for the cytokine classification groups of interest.

If analysis 2 (A and B) or 3 (A, B) result in clinically relevant treatment effect, we will consider the same supportive analyses (I-IV) as listed above.

Sensitivity analyses for 1 (A, B, C), 2 (A) and 3 (A, B):

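### Supportive item IV (mixed model of RMDQ) omits the baseline RMDQ used in the main model, so its one-year contrast is less precise and carries chance baseline imbalance; item I should name its baseline covariate

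*SAP*

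**What the plan says.** All references are to the SAP, in the part on cytokines as predictors of treatment effect (hypothesis 1), unless stated otherwise.

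- **Main model** (Inferential statistics). All six main analyses regress one-year RMDQ on the predictor by treatment interaction, "adjusted for baseline RMDQ score, the potential predictor, the treatment group, the randomization stratification variables".
- **Item I** (Supportive and sensitivity analyses). "Analyses with LBP intensity and ODI score at one year as dependent variables". No covariates are named.
- **Item II**, for contrast. "Analyses with RMDQ score at 3 months follow-up as dependent variable, otherwise similar as above". This item does say that it inherits the model.
- **Item IV**. "Linear mixed effects (LME) models with RMDQ as dependent variable, and 3-part interaction term time x treatment group x cytokine classification group", with time categorical, "adjusted for MC type (1/2) and for former disc herniation surgery (yes/no"). Model specifications are to be chosen by AIC, and the treatment effect comes from pairwise comparison of marginals. The item does not say whether baseline is one of the time levels, whether arm means are held equal at baseline, or at which visit the marginals are compared.
- **Available baselines** (Methods to handle missing data). "We will impute both RMDQ and LBP intensity at baseline, 3 months, 6 months, 9 months and 12 months, ODI score at baseline". RMDQ, LBP intensity and ODI therefore all have a baseline value.

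Under the hypothesis 2 main analyses, the SAP also notes that the baseline score is regarded as among the strongest predictors of later scores.

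**The concern.** Item IV is there to show whether an apparent subgroup effect survives another way of modelling the same outcome. As written, it changes two things at once: it moves to a repeated-measures model and it drops the baseline RMDQ covariate. If the two results disagree, the reader cannot tell whether the model or the lost adjustment is the cause. The cells are small, so a chance baseline difference between arms can be sizeable. The SAP says that interpretation will rest on effect sizes more than p-values, so a shift in the point estimate matters.

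Item I raises a lesser question. It supplies the Table 4 criterion on consistency across related outcomes. The only hypothesis 1 model it could inherit adjusts for baseline RMDQ, not for baseline ODI or baseline LBP intensity.

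**Working it through.** **Inputs from the SAP** (Analyses 2, Table 5A): categories 1+2 have 24 amoxicillin and 13 placebo patients, categories 3+4 have 22 and 19; SD 5; two-sided alpha 0.05; relevance threshold 4 points. **Assumed:** the correlation r between baseline and one-year RMDQ, which the SAP does not give, taken as 0.3 to 0.7; and that SD 5 is the SD before baseline adjustment.

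**1. The plan's own figures reproduce.** The interaction test (noncentral F, 1 and 74 df) has power 0.721 at 6 points (stated 0.72) and detects 6.61 points at 80% power (stated 6.6). The comparison within categories 1+2 (noncentral t) detects 4.96 points (stated 5.0). The SAP gives no power figure for items I or IV.

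**2. What item IV's contrast estimates.** With a free mean for every time, arm and group cell and complete data, the fitted one-year means are the observed means, so other visits do not alter the one-year contrast. On one simulated complete data set (five visits, r = 0.5, the cells above, without the two stratification covariates), the contrast in categories 1+2 was:

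- raw one-year difference: -0.468
- mixed model with baseline as a response: -0.468
- mixed model with follow-up visits only: -0.468
- regression adjusted for baseline: -0.761

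Adjustment for MC type and surgery, and missing visits, would move the mixed-model result slightly away from the raw difference.

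**3. Precision.**

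Unadjusted SE, categories 1+2: 5 × √(1/24 + 1/13) = 1.72.

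Unadjusted SE, interaction: 5 × √(1/24 + 1/13 + 1/22 + 1/19) = 2.33.

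Baseline adjustment multiplies both by √(1 − r²):

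| r | SE, cat. 1+2 | SE, interaction | Unadjusted/adjusted SE | Power at 6 points | Detectable interaction |
|---|---|---|---|---|---|
| none | 1.72 | 2.33 | – | 0.72 | 6.6 |
| 0.3 | 1.64 | 2.22 | 1.05 | 0.76 | 6.3 |
| 0.5 | 1.49 | 2.02 | 1.15 | 0.84 | 5.7 |
| 0.7 | 1.23 | 1.66 | 1.40 | 0.945 | 4.7 |

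**4. Carried imbalance.** The chance baseline difference between 24 and 13 patients has an SE of √(1/24 + 1/13) = 0.34 SD, or 1.7 points at SD 5. In 4,000 simulated trials per value of r, the unadjusted one-year contrast followed the baseline difference with slope 0.33, 0.49 and 0.69 at r = 0.3, 0.5 and 0.7; the adjusted slope was about 0. A one-SE imbalance therefore shifts the unadjusted estimate by 0.344 × r × 5, which is 0.69, 0.86 and 1.03 points at r = 0.4, 0.5 and 0.6.

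**5. Contrasting change from baseline.** The variance factor is 2(1 − r), against 1 − r² with baseline as covariate and 1 for the raw difference. At r = 0.5 these are 1.00, 0.75 and 1.00, so change is no more precise than the raw difference. The SE ratio of change to covariate adjustment is √(2/(1 + r)): 1.24, 1.15 and 1.08 at r = 0.3, 0.5 and 0.7.

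**6. Item I, if it inherits baseline RMDQ.** Let a be the correlation of the outcome with its own baseline (assumed 0.4 to 0.6) and b its correlation with baseline RMDQ (assumed 0.2 to 0.4). The SE ratio of RMDQ-baseline to own-baseline adjustment is √((1 − b²)/(1 − a²)). At a = 0.4, b = 0.4 it is 1.00. At a = 0.6, b = 0.2 it is √(0.96/0.64) = 1.22.

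**The case against.** **Item IV may use baseline in another way.** RMDQ is available at baseline, and if baseline is a response, leaving it off the covariate list is normal practice. This stands as an ambiguity. It does not rescue the one-year contrast, which stays raw unless arm means are held equal at baseline (step 2). A change contrast would use baseline, but less efficiently (step 5), and the SAP's own independence-of-effect paragraph defines the treatment effect as the arm difference in one-year RMDQ. Choosing specifications by AIC does not commit the plan to baseline adjustment.

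**The omission might look deliberate.** The SAP explains why it avoids baseline adjustment, but only for the prognostic analyses of hypothesis 2. For the randomised comparison, its main model does adjust.

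**The figures are borrowed.** This stands. The cells belong to analysis 2. Items I to IV mainly support analyses 1A to 1C, whose subgroups are not yet defined, and for analyses 2 and 3 they are only to be considered. The correlations are assumed.

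**The consequence is limited.** This stands too. Treatment was randomised, so the harm is lost precision and chance imbalance, not systematic bias. Item IV runs only if analysis 1 shows a clinically important difference, and all analyses are declared exploratory.

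**Stronger readings to avoid.** A reader might infer that item I is unadjusted, or is fixed to the wrong instrument's baseline. The text does not say so: item I is silent, and changing the baseline together with the outcome is an equally natural reading. A reader might also infer that item IV feeds the cross-outcome criterion in Table 4. It does not, because its outcome is RMDQ; only item I serves that criterion.

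**Conclusion.** The point holds for item IV. Its written covariate list omits the baseline RMDQ that the main model includes, and its one-year contrast within a cytokine group is then essentially the raw arm difference. Under the assumptions above, the SE is 5 to 40% wider than with adjustment (15% at r = 0.5), and a one-SE baseline imbalance in cells of 24 and 13 moves the estimate by about 0.7 to 1.0 points at r = 0.4 to 0.6, against the 4-point threshold. These sizes are illustrative, since they rest on an assumed correlation and on the analysis 2 cells.

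For item I the point is secondary. The baseline covariate is unnamed, and the SE gain from using the outcome's own baseline ranges from nothing to a ratio of about 1.22 under assumed correlations. Nothing here touches the main analyses.

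**What to change.** **Item IV.** Choose one form and write it down:

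- use RMDQ at 3, 6, 9 and 12 months as responses, with baseline RMDQ and its interaction with time as covariates; or
- keep baseline as a response and constrain the arm means to be equal at baseline within each cytokine group.

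In either form, name the one-year arm difference within group, and its difference between groups, as the contrasts to be reported.

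**Item I.** State that baseline ODI (for ODI) or baseline LBP intensity (for LBP intensity) replaces or joins baseline RMDQ, with the rest of the main model unchanged.

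**Cost.** A few sentences of SAP text; the data are already collected. The first form adds four parameters (one baseline slope for each of four visits) to an already rich model in 78 patients. The second needs none beyond the unconstrained model with baseline as a response, and removes one per cytokine group. Item I needs one covariate swapped or added.

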50 healthy individuals without back pain last 3 months provided blood samples at the blood donor centre (Blodbanken), Oslo University Hospital. All patients and controls provided a written informed consent, and the trial as well as the added project with controls was approved by the Regional Ethics Committee in South East Norway (project 2014/158/REK sør-øst C)

Cytokine measurements

We measured a standard panel of cytokines in serum using a Pro Human Chemokine multi-bead assay (Bio-Rad, Norway). Data was recorded with a Luminex IS 100 instrument (Bio-Rad, Hercules, CA, USA) and protein concentrations were finalized using recombinant standard curves. One cytokine (CXCL5) was not detected in the measurements of most patients and was excluded from the statistical analyses.

Cytokine profiling

In order to identify subsets of subjects based on cytokine profiles, we performed cluster analyses using unsupervised hierarchical clustering and k-means partitioning. We split the heatmap using k-means partitioning of patients and hierarchical clustering of cytokines using the complex heatmap R package (53). Individuals were clustered by using complete linkage of Euclidean distance, and cytokines were clustered using Pearson correlation. The analysis was based on between-subject distances in log-transformed cytokine values standardised to z-scores, thus individuals with shorter distance would more likely be clustered together. The cluster analysis was performed without any post-randomization variable and done prior to any analyses described in this SAP. The results were a classification of patients with MCs into 4 categories (named as category 1 to 4 below) based on their cytokine profile (figure 2) that will be used in the analyses for this SAP.

Figure 1 – Flowchart (with numbers relevant for cytokine measurements in red)

[figure not shown]
[figure not shown]

Figure 2 -Heatmap of cytokine levels with classification of patients based on unsupervised hierarchical clustering using k-means partitioning

The heatmap X-axis shows patients (ordered by clustering based on complete linkage with Euclidean distance measure), and the Y-axis shows cytokines (ordered by clustering based on Pearson correlation as distance measure). The top colour row highlights the 4 categories of patients which will be used in analyses

Objectives

The objectives covered in the present Statistical Analysis Plan are:

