In stage 2, a regression analysis (as described above) will be performed (n=78), where the potential predictor of treatment effect of interest will be defined based on the results of the stage 1 analyses. Each of the three stage 1 analyses (A, B and C) will result in one regression analysis that we will perform in prioritized order (1A, 1B and 1C, respectively).

Analyses 2, based on prespecified subgroups

We will use the same regression statistical model for the analyses 2 (n=78), with the cytokine classification group (4 categories of patients, figure 2) as the potential predictor of treatment effect. The classification group variable will be dichotomized into category 1 and 2 vs category 3 and 4. We hypothesize a treatment effect of antibiotics in the combined classification category 1 and 2.

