-Due to power limitations we will restrict the number of covariates/independent variables to eight (10 patients/independent variable)(63). Based on suspected prognostic factors for LBP disability (61, 62) and suspected factors associated with serum cytokine levels (64, 65), we will add the following as covariates into the model due to possible confounding: age, leg pain (0-10 NRS), fear avoidance, emotional distress (dichotomized into HSCL-25 $\geq 1,75$ and $< 1,75$), psychiatric comorbidity (yes/no), other specific comorbidity (numerical, one point for each of rheumatoid arthritis, osteoarthritis, Diabetic, Cardiac/pulmonary) and sick leave (categorized into 1. working full time, 2. partial sick leave and 3. complete sick leave / disability pension / unemployed / student/other/unknown). Age, leg pain and fear avoidance will be continuous variables.

For each model we will evaluate:

1. The predictiveness by comparing the multiple correlation coefficient R^2 of the complete model with the R^2 in the model without the independent variable of interest (66).
2. The effect size described in terms of relative change in RMDQ. We will consider effect size $>30\%$ as clinically relevant, which equates approximately to a difference of 4 out of 12.8 (at baseline) RMDQ points.

The following models (1, 2A, 2B, 3, 4A, 4B, 5A, 5B, 5C, 5D, 5E) will differ in choice of independent variable of interest, which will be:

1. Cytokine category group based on cytokine classification group (4 categories of patients, figure 2). Each category of patients will be assessed versus the three other categories combined.
2. Classification variable defined by a Recursive Partitioning analysis using RPART command in R. Relative change in RMDQ from baseline to one-year follow-up will be dependent variable. Only patients nonmissing values in both baseline and one-year follow-up RMDQ score will be included. Stopping conditions will be $\text{maxdepth}=3$ and n_{min} (minimal number of observations in terminal/leaf node)=5. We will use tenfold cross-validation and a complexity parameter of 0,01. We will perform two Recursive Partitioning models that differs only in what variables that are included:

Statistical Analysis Plan for analysis of cytokines as prognostic factors and predictors of antibiotic treatment effect in patients with chronic low back pain and Modic changes (the AIM trial) - - version 1.0

- A. all 39 cytokines

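### Supportive mixed model (item IV) for analyses 1A-1C is written with the figure 2 cluster groups, not the stage 1 subgroup that triggers it, so it gives at best indirect evidence on that subgroup over time

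*SAP*

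**What the plan says.** The list of supportive analyses for hypothesis 1 opens with "As supportive analyses for 1 (A, B and C), we will perform" (item I). Items II to IV are conditional: "If clinically important differences between the treatment groups in analysis 1 (A, B and C), we will also perform the following supportive analyses". Item IV is a linear mixed model for RMDQ containing a "3-part interaction term time x treatment group x cytokine classification group (treating time as a categorical variable". From the selected model, "we will do a pairwise comparison of marginals to estimate the treatment effect for the cytokine classification groups of interest". The list ends by saying that the same items will be considered if analysis 2 or 3 gives a clinically relevant effect.

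The predictor in 1A-1C is described under Analyses 1. Stage 1 partitions patients recursively, and stage 2 enters the resulting subgroup in the regression. Table 2 states that these subgroups do not exist yet.

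The term used in item IV appears elsewhere with a fixed meaning. Analyses 2 is run "with the cytokine classification group (4 categories of patients, figure 2) as the potential predictor of treatment effect". Model 1 of hypothesis 2 uses "Cytokine category group based on cytokine classification group (4 categories of patients, figure 2". The section on cytokine profiling says that the clustering, done before any analysis in the SAP, produced a "classification of patients with MCs into 4 categories (named as category 1 to 4 below) based on their cytokine profile".

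**The concern.** Item IV is started by a result for one grouping and then fits another. An analyst who follows the text would find a clinically important effect in, say, the 1A subgroup and then plot treatment effects over time in the figure 2 clusters.

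What is at stake is a check on the three top-ranked analyses. Their subgroups are data-driven, come from 73 patients with a minimum size of 5, and are tested without multiplicity adjustment. A check over time is most useful there if it follows the same subgroup. Item IV is the only supportive analysis for hypothesis 1 that models RMDQ across the follow-up visits; item II looks at 3 months alone. The text also leaves the analyst to decide, after seeing the 1A-1C results, which grouping to put in the model.

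**Working it through.** No stated figure is in dispute. The check traces one term through the SAP and then illustrates what the substitution could do.

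**Step 1: what triggers item IV.** A clinically important difference in 1A, 1B or 1C. The predictor there is the stage 1 subgroup, built from nine cytokines (1A), those nine plus age and the STIR composite (1B), or all 39 cytokines (1C).

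**Step 2: what item IV models.** The cytokine classification group, both in the three-way term and in the marginal comparison.

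**Step 3: what that term means in the SAP.**
- Analyses 2: the four figure 2 categories, stated in parentheses.
- Hypothesis 2, model 1: the same parenthesis.
- Imputation model: the term stands without the parenthesis in the list "cytokine classification group, principal component 1 (from analyses 3 A and B under analyses of hypothesis 1), treatment group". It is a variable that already exists and is distinct from PC1. No stage 1 subgroup is listed.

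**Step 4: comparison.** Steps 1 and 2 name different variables, and no sentence puts the stage 1 subgroup in place of the clusters. The mismatch is plainest for 1B, whose subgroup may be defined partly or wholly by age or STIR.

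**Step 5: the other analyses, if the list is reused.** For 2A the variable is essentially right, but the term as defined has four levels whereas analysis 2A uses categories 1+2 versus 3+4. In Table 5A, category 1 holds 5 amoxicillin and 3 placebo patients. For 3A and 3B the predictor is PC1, a continuous score, so neither the cluster term nor a pairwise group comparison fits.

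**Step 6: illustration of dilution.** I first reproduced the SAP's own interaction power for analysis 2. Cell sizes from Table 5A are 13 placebo and 24 amoxicillin in categories 1+2, and 19 and 22 in categories 3+4; SD is 5.
- SE of the interaction = 5 × √(1/13 + 1/24 + 1/19 + 1/22) = 5 × √0.2167 = 2.33.
- With the noncentral F distribution (1 and 78 − 4 = 74 df), power at 6 points is 0.7205 (SAP: 0.72), and the difference detectable with 80% power is 6.61 (SAP: 6.6).

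Now suppose that the treatment effect differs by 6 points between patients inside and outside the stage 1 subgroup S, and depends on nothing else. The contrast seen between the cluster groups is then

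6 × [P(S | categories 1+2) − P(S | categories 3+4)].

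The difference in shares is an assumption, because the SAP gives no figure for it:

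| Difference in share of S | Cluster contrast (RMDQ points) | Power |
|---|---|---|
| 0 | 0 | 0.05 |
| 0.25 | 1.5 | 0.10 |
| 0.50 | 3.0 | 0.25 |
| 0.75 | 4.5 | 0.48 |
| 1 | 6.0 | 0.72 |

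This uses one-year values and the two-group form of the clusters. It does not reproduce the mixed model. It shows only that what the cluster model says about S depends on the overlap.

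**The case against.** **The wording may be generic.** Stage 1 is itself described as classifying patients into categories. Hypothesis 2 calls its recursive-partitioning result a classification variable, and Table 2 applies the word classification even to PC1. Item IV lacks the figure 2 parenthesis, ends with groups of interest, and sits in a list written for analysis 1 and reusable for analysis 3. The authors may well have meant the groups of whichever analysis is being supported. This stands as a possible reading of intent. It does not settle the text: the imputation section uses the bare term for an existing variable, and elsewhere the SAP has general expressions, such as potential predictor, that item IV does not use. If the generic meaning was intended, the wording still needs correcting.

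**A reader might infer that item IV can say nothing about the 1A-1C subgroup.** The documents do not support that. Clusters and stage 1 subgroups are both built from baseline cytokines (with age and STIR added in 1B), so some overlap is plausible. Support is then diluted, and is absent only if the two groupings are unrelated.

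**A reader might also infer that a mined subgroup would end up wrongly accepted or rejected.** That does not follow either. Items I and II carry over the predictor of the main analysis, and item III is not tied to the clusters. The independence analysis uses the actual predictors. The credibility criteria in Table 4 do not include consistency over time. The plan is declared exploratory, and any predictor is to be confirmed in later studies. For analyses 2 and 3 the list is only to be considered, so there is no firm commitment to a wrong model there. All of this stands and limits the weight of the point.

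**Conclusion.** The point holds in a limited form. Read by the SAP's own definition, item IV tests the grouping of analysis 2 while being triggered by analysis 1. Its results would be at best indirect, diluted evidence on whether a 1A-1C subgroup effect persists over time.

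The size cannot be fixed from the documents. Under the assumed 6-point interaction, the share of it visible in the clusters runs from none to all, depending on an overlap that the SAP does not report. The table in the working is an illustration and not an estimate of harm.

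The consequence stays within one conditional supportive analysis. No main estimate, interaction test or stated credibility criterion changes. The conclusion assumes that the term carries the meaning given under Analyses 2 and hypothesis 2, model 1; if it was meant generically, what remains is an ambiguity that the same edit removes.

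**What to change.** In item IV, replace cytokine classification group by the predictor of the analysis being supported, and spell it out:
- 1A, 1B, 1C: the stage 1 subgroup of that analysis;
- 2A, if the list is used: categories 1+2 versus 3+4;
- 3A, 3B, if the list is used: PC1 of that analysis.

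Make the same change in the sentence on marginal comparisons. For PC1, which is continuous, estimate the treatment effect at stated PC1 values instead of by pairwise comparison of groups.

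The cost is wording only: no new data and no change to any main analysis. The edit should be made before the 1A-1C results are seen, so that the choice of grouping cannot depend on them.
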